9.0 Privacy/Confidentiality Issues

All measures will be taken to ensure participant confidentiality during all phases of data collection, storage, and management. All patient data will be assigned a study ID number at the time of collection. Until the medical chart abstraction has been completed for all patients, a master key that contains patients name and date of birth or medical record number will be maintained on the secure VUMC server, in a password protected folder to which only the PI and mentors and approved study personnel have access. Once all data is collected for each individual participant, the linking information and their entry on the master key will be destroyed. The PI will subsequently maintain all de-identified data that is collected in this study. Hard copies will be kept separately in a locked file cabinet in the PI's or research coordinator's office. All materials will have a study ID number and no identifying information will be attached to any data (i.e., no names, address, phone number, medical record, social security number, or date of birth). A database will be created with the de- identified data and maintained by the PI in a password-protected folder on the Vanderbilt Redcap database. All video/audio recordings will be stored on the secure VUMC server. Only the KSP included in this IRB application will have access to the research information. This project will utilize the REDCap platform for data collection and management. This includes the ability for project team members listed as Key Study Personnel with existing electronic health record (EHR) system access rights to make use of REDCap Clinical Data Interoperability Services (CDIS) tools. These tools are designed to enable transfer of relevant study-related data from the Vanderbilt Research Derivative and/or directly from the EHR into REDCap.

10.0 Follow-up and Record Retention

Study duration is 2 years. Once all data is collected for each individual participant, the linking information and their entry on the master key will be destroyed. The raw data will be stored for 10 years after the close of the study.

## MoVE R03 Pilot Study Analysis Plan for Aim 2A

The primary aim of this study were to gather feasibility metrics for a larger trial. However, Aim 2A included an estimates of treatment effects, acknowledging these will be underpowered in this pilot study. **Aim 2A: To generate estimates of treatment effects and variation of a culturally tailored motivational interviewing protocol as compared to usual dialysis care and to evaluate feasibility outcomes and acceptability.**

**Study Design and Setting:** A three-month randomized pilot feasibility trial. I will enroll N=30 patients from the VUMC-owned dialysis unit of over 300 patients, 60 to 70% of whom self-identify as African American.

**Inclusion Criteria:** English-speaking African American receiving hemodialysis who are  $\geq 18$  years of age who have missed more than one dialysis session per month in any of the three-months prior to enrollment or who have shortened their dialysis session by over ten minutes per month. Participants with missed treatments due to hospitalizations or excused travel, with alternate arrangements for dialysis will not be included.

**Exclusion Criteria:** Non-English speaking; known diagnosis of dementia or psychotic illness; severe medical illness; no documented evidence of hemodialysis treatment non-adherence.

**Randomization & Masking:** Randomization will be performed within the REDCap online, secure, data management platform, and personnel will be masked until after enrollment. Patients will be randomized to receive Culturally Tailored Motivational Interviewing (Arm 1) or to Usual Care (Arm 2) using a block randomization scheme. Personnel collecting surveys will be masked to the assignment.

**Outcomes:** In this pilot feasibility trial, emphasis will be placed on assessing preliminary operational feasibility. Study outcomes will include assessing screening to enrollment ratio; attendance to motivational interviewing sessions; motivational interviewing fidelity, and drop-out rates. Outcomes will also include imprecise measures of variation in hemodialysis treatment adherence and motivation-related factors including the following: *autonomous regulation, autonomy support, and perceived competence* using the Autonomous Regulation (AR) scale; Health Care Climate Questionnaire (HCC) and Perceived Competence (PC) scales, respectively. Apathy and optimism will be assessed with the Apathy Evaluation scale (AES) (range 0-4) and the optimism subscale of the Perceived Expectancies index (PEI) (range 0-5).

**Analysis Plan:** Descriptive measures of autonomy, apathy, optimism, and dialysis treatment adherence will be calculated, including sample means, standard deviations, and quantiles. Estimated distributions of these variables will guide study design and power for a follow-up confirmatory clinical trial. Graphical displays of univariate and bivariate data will be created to generate hypotheses for the follow-up study. Preliminary estimates of treatment effect sizes will be calculated via multivariate linear regressions adjusting for the baseline measure of the outcome, i.e.  $Y_{8wks} \sim \text{treatment} + f(Y_{0wks})$ , where  $f()$  is a 3rd degree polynomial when adjusting for baseline adherence and a linear fit when adjusting for other baseline measures. We will report 95% Wald confidence intervals for the treatment effect.

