7.0 Study Withdrawal/Discontinuation

If the study participant decides to withdraw from the study, no additional information will be collected from them. This will have no impact on the care that they receive from their doctor. They are allowing us to use their information from this study for as long as we want. If they decide to withdraw permission, all they need to do is to let [name] know. A decision to not participate in this research will not affect their treatment.

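### Do the SAP's 95% Wald intervals fall short of 95% coverage because no t distribution is named?

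*SAP*

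**What the plan says.** The Analysis Plan paragraph of the SAP states: "Preliminary estimates of treatment effect sizes will be calculated via multivariate linear regressions adjusting for the baseline measure of the outcome". The outcome is the 8-week value, and the predictors are treatment and a function of the baseline value. That function is a third-"degree polynomial when adjusting for baseline adherence and a linear fit when adjusting for other baseline measures". The paragraph ends: "We will report 95% Wald confidence intervals for the treatment effect".

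The size is set under Study Design and Setting: "I will enroll N=30 patients". Section 7.0 of the Protocol bears on how many reach the analysis: "If the study participant decides to withdraw from the study, no additional information will be collected from them".

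Neither document gives a multiplier, a reference distribution, residual degrees of freedom or a variance estimator. Section 8.0 of the Protocol does not mention confidence intervals. On the standing of the effect estimates, the opening of the SAP is candid, "acknowledging these will be underpowered in this pilot study", and it puts feasibility first.

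**The concern.** In many texts a Wald interval is the large-sample form: the estimate plus or minus 1.96 standard errors. That form treats the residual variance as known. With at most 30 patients and up to five coefficients the variance is estimated from few degrees of freedom, so 1.96 is too small and an interval labelled 95% covers less than 95%. The shortfall always runs in the same direction, and it grows if patients are lost before week 8.

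These intervals are the only measure of uncertainty that the SAP attaches to the treatment effects, and estimating those effects is part of Aim 2A. If they were materially too narrow, the pilot would overstate how well it had pinned down the effect, and that impression could carry into the planning of the follow-on efficacy trial.

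**Working it through.** **Inputs**
- Patients: n = 30 at most (SAP, Study Design and Setting).
- Coefficients, from the model in the SAP, Analysis Plan. Adherence: intercept + treatment + three baseline terms, k = 5. Other outcomes: intercept + treatment + one baseline term, k = 3.
- Drop-out: the documents give no expected rate. The rows for 24 and 20 analysed assume losses of 6/30 = 20% and 10/30 = 33%.
- Allocation ratio: not stated. It does not enter the degrees of freedom or this calculation.

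**Formulas.** In a linear model with normal, equal-variance errors and the usual residual variance, (estimate − true effect)/SE follows t on df = n − k. Hence:
- coverage of estimate ± 1.960 SE = P(|t_df| < 1.960);
- relative width of the t interval = t_df(0.975)/1.960.

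**The plan's own figure.** The stated level is 95%. With the t multiplier it is reproduced exactly, because P(|t_df| < t_df(0.975)) = 0.95 by definition. With 1.960 it is not. The SAP does not say which of the two it means.

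**Results**

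| Analysed | Outcome | df = n − k | t multiplier | Coverage with 1.960 | t interval wider by |
|---|---|---|---|---|---|
| 30 | Adherence | 30 − 5 = 25 | 2.0595 | 93.9% | 5.1% |
| 30 | Other | 30 − 3 = 27 | 2.0518 | 94.0% | 4.7% |
| 24 | Adherence | 24 − 5 = 19 | 2.0930 | 93.5% | 6.8% |
| 24 | Other | 24 − 3 = 21 | 2.0796 | 93.7% | 6.1% |
| 20 | Adherence | 20 − 5 = 15 | 2.1314 | 93.1% | 8.7% |
| 20 | Other | 20 − 3 = 17 | 2.1098 | 93.3% | 7.6% |

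For example, the first row is 2.0595/1.9600 = 1.051, so 5.1% wider.

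**Check by simulation.** With 50,000 simulated trials per model (30 patients, 15 per arm, normal errors), the 1.960 interval covered 94.1% with the cubic baseline and 94.2% with the linear one, within about 0.2 points of the exact values. The t interval, scored on the first 5,000 of those trials, covered 95.2% and 95.3%.

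**What it means in use.** With 30 analysed, the half-width for adherence would be 1.960 SE instead of 2.060 SE, a difference of 0.10 SE. About one more interval in a hundred would miss the true effect.

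**The case for a change.** The best argument for a change is that it costs one phrase. As written, two analysts could follow the SAP faithfully and report different intervals from the same data. Naming t would remove that freedom and give the stated level under the model. An analyst who took large-sample theory further and divided the residual sum of squares by n, not by n − k, would fall to 91.4% (adherence) and 92.6% (other outcomes) with 30 patients.

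Part of this stands: the reference distribution is not written down, and the arithmetic is right. Three things limit it.

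First, the shortfall depends on a multiplier that the SAP never states. An estimate plus or minus a quantile times its standard error is still called a Wald interval when the quantile comes from t, and that is the routine calculation for a linear-regression coefficient. The 91–93% figures need a further departure, a variance estimator that the plan does not mention and that is not usual for linear regression.

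Second, nothing turns on the difference. The plan has no hypothesis test, success threshold or progression rule. The SAP says that the estimated distributions of the measures will guide the design and power of the next trial; it does not give these intervals that role.

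Third, the promise of exactly 95% from t holds only under normal, equal-variance errors. The apathy and optimism measures are bounded scales (0–4 and 0–5 in the SAP), and adherence is studied in patients selected for recent missed or shortened sessions. The documents give no ground for assuming normality. Departures from it could move coverage by an amount comparable to the one point at issue; that was not calculated here.

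**Conclusion.** No change follows. The SAP leaves the reference distribution unstated, but it does not commit to 1.96, so the documents do not show that the planned intervals are wrong. An analyst fitting these regressions would ordinarily use t on the residual degrees of freedom, and there is then no shortfall.

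On the unfavourable reading, the loss with all 30 analysed is 95.0 − 93.9 = 1.1 points for adherence and 95.0 − 94.0 = 1.0 point for the other outcomes. It reaches 1.9 and 1.7 points only if a third of the patients are lost, a rate assumed here and not taken from the documents. These figures rest on normal, equal-variance errors and the usual residual variance. A difference of this size, on estimates presented as preliminary and underpowered, would not alter any conclusion that the pilot is designed to reach.
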